15.3.6.1. Adverse Events

All AEs will be coded using Medical Dictionary for Regulatory Activities (MedDRA) version 18.0 or higher. AEs are untoward medical occurrences:

- that occurred on or after the first dose of study medication,
- with a missing start date and a stop date on or after the first dose of study medication, or
- with both a missing start and stop date.

AEs will be summarized by treatment and by MedDRA system organ class (SOC) and Preferred Term (PT).

The following AEs will be summarized and presented by treatment group and by MedDRA SOC and PT for the Safety population:

- All AEs (including number of events and subject incidence).
- Serious AEs.
- AEs leading to discontinuation.
- AEs by maximum severity (mild, moderate, severe).
- AEs by relationship to the study treatment (related, or not related).
- Serious AEs by relationship to the study treatment.
- AEs leading to death.

The following conventions will be followed in summarizing AEs:

- For subject incidence summaries, each subject will be counted only once within each SOC and within each preferred term.

- If a subject reports more than one AE within a preferred term and/or a body system, the AE with the highest known severity within each body system and within each preferred term will be included in the summaries by severity.
- For summaries by relationship to the study medication, AEs will be grouped as “related” or “not related.” AEs assessed as “possible,” “probable,” or “definite,” will be grouped as “related.” If a subject reports more than one AE within the same treatment regimen, SOC and PT, and any are related, it will be summarized as related. AEs whose relationship to treatment is assessed as “not related” or “unlikely” will be grouped as “not related.”

A listing of AEs, as well as a listing of deaths, SAEs, or AEs leading to discontinuation, will be presented.

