8.4 Adverse Events

All AEs will be coded using MedDRA Version 19.0. An AE is any untoward medical occurrence:

- that occurred before, on or after the first dose of study medication,
- with a missing start date and a stop date before, on or after the first dose of study medication, or
- with both a missing start and stop date.

Untoward medical occurrences that occur between the time of informed consent/assent and first study drug administration are pre-treatment events. Those that occur after first administration of study drug are considered AEs. Clinically significant abnormal objective findings (eg, clinical laboratory value, ECG value, and physical examination observation) will also be recorded as AEs.

A serious adverse event (SAE) is an AE that meets one or more of the following criteria:

- Results in death.
- Is life threatening.
- Requires hospitalization or prolongation of existing hospitalization.
- Results in persistent or significant disability or incapacity.
- Is a congenital anomaly or birth defect.
- Is an important medical event that may jeopardize the subject or may require a medical or surgical intervention to prevent one of the outcomes listed

above. Examples of such medical events include allergic bronchospasm requiring intensive treatment in an emergency room or at home, blood dyscrasias or convulsions that do not result in inpatient hospitalization.

An AE is considered treatment emergent if it started during or after administration of the first dose of study medication. In addition, medical history events that worsen in severity after the start of dosing will be considered treatment-emergent adverse events (TEAEs). If a subject discontinues early from the study and has an AE after his/her last dosing date, the AE will be deemed as treatment emergent if it occurs ≤ 72 hours after the last dose and not as treatment emergent if it occurs >72 hours after the last dose of study medication. AEs with partial start dates will be imputed as outlined in Section 8.1 and assigned to the associated treatment period.

Summary Tabulations

An overview of the frequency, i.e., the number and percentage of subjects and events with at least one of the following AEs, will be presented by treatment group (placebo, dasotraline 4 mg/day, dasotraline 6 mg/day, and combined dasotraline [4 mg/day + 6 mg/day]):

- All TEAEs
- SAEs
- TEAEs leading to discontinuation
- Severe TEAEs
- TEAEs related to study medication
- Severe TEAEs

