- SAEs related to study medication
- AEs leading to death

System Organ Class and Preferred Term Tabulations

The frequency of subjects reporting TEAEs, along with the frequency of events, will be summarized within each system organ class (SOC) and preferred term (PT) by treatment group. The SOC terms and PTs will be presented in decreasing order of the total number of subjects in the combined dasotraline group (4 mg/day and 6 mg/day)

(frequency) who experienced each AE. System organ class terms and PTs with the same frequency will be presented alphabetically.

Each subject will be counted only once within each SOC and within each PT. If a single subject experienced the same AE more than once within a treatment period, the subject will be counted once per SOC and PT for that AE. For subjects that experienced AEs with multiple severities, the AE with the highest known severity within each SOC and PT will be counted. Adverse events with unassigned/unknown severity will be categorized as severe.

For summaries by relationship to the study medication, AEs will be grouped as “related” or “not related.” AEs assessed as “possible,” “probable,” or “definite,” will be grouped as “related.” If a subject reports more than one AE within the same treatment regimen, SOC and PT, and any are related, it will be summarized as related. AEs whose relationship to treatment is assessed as “not related” or “unlikely” will be grouped as “not related.” Events with unassigned/unknown relationship to study medication will be considered related to study medication.

The frequency of subjects reporting the following AEs, along with the frequency of events, will be summarized and presented by treatment group and MedDRA SOC and PT for the Safety population:

- All TEAEs (including number of events and subject incidence)
- SAEs
- Non-SAEs
- TEAEs leading to discontinuation
- TEAEs by maximum severity (mild, moderate, severe)
- TEAEs by relationship to the study treatment (related, or not related)
- SAEs by relationship to the study treatment
- AEs leading to death

By-Subject Listings

By-subject listings including relevant information (i.e. treatment, age, sex, race, duration of AE, severity, relationship, outcome, action taken, etc.) will be presented for:

- All AEs
- SAEs
- AEs leading to death
- AEs leading to discontinuation (per the case report form)

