8.5 Adverse Events of Special Concern

Adverse events of special concern for this study are defined as neuropsychiatric and mania related AEs such as ideas of reference; illogical thinking; illusion; childhood psychosis; abnormal behaviour; psychotic disorder; hallucination; hallucination, auditory; hallucination, gustatory; hallucination, olfactory; hallucination, tactile; hallucination, visual; hallucinations, mixed; hypnagogic hallucination; hypnopompic hallucination; somatic hallucination; hallucination, synaesthetic; formication; paranoia; catatonia; delusion; delusional perception; somatic delusion; suspiciousness; tangentiality; thinking abnormal; thought blocking; thought insertion; thought withdrawal; substance-induced psychotic disorder; acute psychosis; delusion of grandeur; delusion of reference; delusion of replacement; derailment; echolalia; echopraxia; erotomanic delusion; jealous delusion; loose associations; magical thinking; persecutory delusion; psychotic behavior; brief psychotic disorder with marked stressors; thought broadcasting; reactive psychosis; impaired reasoning; disorganized speech; mixed delusion; intrusive thoughts; transient psychosis; brief psychotic disorder without marked stressors; mania; hypomania; and substance-induced mood disorder. AEs of special concern will be summarized by PT and treatment group.

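### SAP 8.4 stops counting treatment-emergent AEs 72 hours after the last dose for early discontinuers only, which departs from protocol 15.3.6.1 and is not declared in SAP 12.2

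*SAP*

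**What the plan says.** SAP 8.4 opens with a rule that has no upper time limit: "An AE is considered treatment emergent if it started during or after administration of the first dose of study medication". Medical history that worsens after dosing starts also counts. The next rule covers one group only. It begins "If a subject discontinues early from the study and has an AE after his/her last dosing date" and keeps such an event as treatment-emergent up to 72 hours after the last dose, "and not as treatment emergent if it occurs >72 hours after the last dose of study medication". No limit is set for completers and no reason is given for 72 hours.

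Protocol 15.3.6.1 defines the AEs to be analysed as, among others, those "that occurred on or after the first dose of study medication", without an upper limit or a split by completion status. The first table it plans is "All AEs (including number of events and subject incidence". The matching table in SAP 8.4 is "All TEAEs (including number of events and subject incidence", and the severity and relationship tables are likewise restricted to TEAEs. SAP 12.2 states that nothing in the planned analysis has changed.

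On follow-up, protocol 11.5.3 asks every subject, including those who stop drug early, to return 7 (±2) days after the last dose. Protocol 12.1.1 collects AEs to the last study visit. SAP 8.3 provides for subjects who leave the study early and still come back.

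**The concern.** Whether a late event enters the main safety tables should depend on the event and its timing, not on whether the child finished the study. Under SAP 8.4 it depends on completion status. A new event, or a worsening recorded as a new AE, that starts between 72 hours and the End of Study (EOS) visit is kept for a completer and dropped for an early discontinuer.

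The trigger is also loosely defined. It is leaving the study, not stopping drug. Protocol 17.3 expects that a child may stop drug and still attend to the final visit, and such a child need not fall under the exception. Two children with the same last dose day and the same late event could then be classified differently.

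At stake are the TEAE tables: overall, by system organ class and preferred term, by maximum severity and by relationship. The rule can only lower counts there, and only among those who left early. If early discontinuation differed by arm, the arm comparison in those tables would be distorted. The documents do not say whether it does.

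**Working it through.** The plan gives no figure to reproduce. The check is a comparison of the texts, followed by a sizing.

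**1. One event under each rule.** Take an AE starting 5 days after the last dose, 5 × 24 = 120 h.
- Completer, SAP 8.4: no upper limit, so a TEAE.
- Early discontinuer who returns, SAP 8.4: 120 h > 72 h, so not a TEAE.
- Protocol 15.3.6.1: both are counted.

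**2. Share of post-dose follow-up treated differently.** For a return d days after the last dose, the share is (24d − 72) / 24d.
- d = 5: 48/120 = 40%
- d = 7: 96/168 = 57%
- d = 9: 144/216 = 67%

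**3. Child-days cut, 4 mg/day and placebo.** Inputs:
- 110 subjects randomized in an attempt to have 100 complete (SAP 2.6), so 10 planned non-completers (9.1%).
- Doses on Days 1 to 14 (protocol 10.1), so 13 days from first to last dose.
- EOS return at d = 5, 7 or 9 days.

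Formulas:
- Days cut per returning discontinuer = d − 3.
- AE follow-up of a completer = 13 + d.
- AE follow-up of a returning discontinuer = d to 13 + d, depending on when drug was stopped.
- AE follow-up of a non-returning discontinuer = 0 to 13 (assumed followed only while on drug).

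With all 10 returning at d = 7, days cut = 10 × 4 = 40. Total follow-up is 100 × 20 + 10 × 20 = 2200 at most and 100 × 20 + 10 × 7 = 2070 at least.

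| Scenario | d | Days cut | Share of AE follow-up |
|---|---|---|---|
| All 10 return | 5 | 20 | 20/1980 to 20/1850 = 1.01% to 1.08% |
| All 10 return | 7 | 40 | 40/2200 to 40/2070 = 1.82% to 1.93% |
| All 10 return | 9 | 60 | 60/2420 to 60/2290 = 2.48% to 2.62% |
| 5 of 10 return (assumed) | 5 | 10 | 10/1955 to 10/1825 = 0.51% to 0.55% |
| 5 of 10 return (assumed) | 7 | 20 | 20/2165 to 20/2035 = 0.92% to 0.98% |
| 5 of 10 return (assumed) | 9 | 30 | 30/2375 to 30/2245 = 1.26% to 1.34% |
| None returns | any | 0 | about 0 |

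**4. Adding 6 mg/day.** About 20 subjects were randomized to it, and no dropout figure is given. At the same 9.1% (assumed), 20 × 0.091 = 1.8, taken as 2, all returning. That adds 2 × 4 = 8 child-days at d = 7 (4 at d = 5, 12 at d = 9). For all three groups:
- d = 7: 48/2600 to 48/2444 = 1.85% to 1.96%
- d = 5: 24/2340 to 24/2184 = 1.03% to 1.10%
- d = 9: 72/2860 to 72/2704 = 2.52% to 2.66%

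With 0 to 5 discontinuers at 6 mg/day, the addition at d = 7 is 0 to 20 child-days.

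**5. Does the drug's elimination explain 72 hours?** Protocol 4.2 reports a median half-life of 56 to 84 h after single doses in children and adolescents. So 72 h is 72/84 = 0.86 to 72/56 = 1.29 half-lives. Under first-order elimination (assumed), 41% to 55% of the drug would remain. The cut-off does not mark the end of exposure.

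**The case against.** The strongest reply is that little is lost.
- The tables are descriptive, and no test or stopping rule in the documents uses the flag.
- An AE that began on drug stays a TEAE, and AEs leading to discontinuation would rarely be touched.
- SAP 8.4 also tabulates SAEs, non-serious AEs and deaths and lists all AEs. None of these is worded as limited to TEAEs. Nor is the special-concern table in SAP 8.5 ("AEs of special concern will be summarized by PT and treatment group").
- Event counts from the SAE and Non-SAE tables can be added to give total events.

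All of this stands and limits the consequence. Subject incidence, however, cannot be rebuilt by addition, because one child may appear in both tables. The two counts only bound it, between the larger count and their sum. The protocol's table asks for incidence as well as events.

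A second reply is that the affected group is uncertain. Protocol Table 5 defines a completed subject as one followed through the last visit, so a child who stops drug but attends EOS might not count as having left the study. That may shrink the group. It also shows that the rule does not say clearly whom it covers.

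Third, the 10 non-completers come from a recruitment target, and protocol 13.1 allows replacement of subjects who leave, so more than 10 could leave. This is fair: the 40 child-days are conditional on 10, not an absolute maximum.

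Finally, the protocol does not use the term TEAE and leaves detail to the SAP. Even so, replacing its planned all-AE tables with a narrower set is a change of analysis and belongs in SAP 12.2.

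**Conclusion.** The concern holds. As written, SAP 8.4 classifies the same late event differently by completion status, departs from protocol 15.3.6.1, gives no reason for 72 hours and is not declared.

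The size is probably small. It runs from about 0 if no early discontinuer returns to 40 child-days, about 1.8% to 1.9% of AE follow-up in the 4 mg/day and placebo groups, if 10 leave the study and all return at 7 days. Over the visit window the full-return figure is 20 to 60 child-days (1.0% to 2.6%). With 6 mg/day included under the assumptions shown, it is 24 to 72 child-days (1.0% to 2.7%). These are shares of follow-up time, not of events. The documents give no rate of late AEs, so the number of events affected cannot be stated. Bias between arms requires unequal early discontinuation, which the documents do not report. The point does not touch the efficacy analysis, but it should be corrected because the affected tables are the main safety summaries.

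**What to change.** Delete the 72-hour sentence from SAP 8.4. One rule then applies to every subject: an AE starting, or medical history worsening, on or after the first dose. That agrees with protocol 15.3.6.1 on this point.

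If the sponsor wants a post-dose limit, apply the same limit to completers and discontinuers, give the reason for its length and declare it in SAP 12.2.

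The cost is one SAP sentence and one derivation flag, and the data are already collected. The drawback of deletion is that a few events may be counted in discontinuers who restart another ADHD treatment before EOS, whereas protocol 10.3.1 bars completers from such treatment through that visit. Those events can be identified from the concomitant medication records and the AE listings.

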8.5 Adverse Events of Special Concern

Adverse events of special concern for this study are defined as neuropsychiatric and mania related AEs such as ideas of reference; illogical thinking; illusion; childhood psychosis; abnormal behaviour; psychotic disorder; hallucination; hallucination, auditory; hallucination, gustatory; hallucination, olfactory; hallucination, tactile; hallucination, visual; hallucinations, mixed; hypnagogic hallucination; hypnopompic hallucination; somatic hallucination; hallucination, synaesthetic; formication; paranoia; catatonia; delusion; delusional perception; somatic delusion; suspiciousness; tangentiality; thinking abnormal; thought blocking; thought insertion; thought withdrawal; substance-induced psychotic disorder; acute psychosis; delusion of grandeur; delusion of reference; delusion of replacement; derailment; echolalia; echopraxia; erotomanic delusion; jealous delusion; loose associations; magical thinking; persecutory delusion; psychotic behavior; brief psychotic disorder with marked stressors; thought broadcasting; reactive psychosis; impaired reasoning; disorganized speech; mixed delusion; intrusive thoughts; transient psychosis; brief psychotic disorder without marked stressors; mania; hypomania; and substance-induced mood disorder. AEs of special concern will be summarized by PT and treatment group.

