10. OTHER ANALYSES

Data collected for the 6 mg/day dasotraline arm will be used for exploratory analyses. All subjects in the 6 mg/day arm will be analyzed using the same primary and secondary efficacy analysis methods described in Section 7.5 in a separate model from the 4 mg/day arm. They will also be analyzed for safety as described in Section 8, both separately and pooled with the 4 mg/day dasotraline group.

Dose response and tolerability for dasotraline treated subjects will also be analyzed in a weight-based dose-level analysis. Dose per weight (mg/kg) will be calculated for each dasotraline treated subject and then placed into the following groupings:

- 2 equal-sized groups: 2 groups will be formed based on the median number of dasotraline treated subjects. Each group will contain half of the population of dasotraline treated subjects.
- 3 equal-sized groups: 3 groups will be formed based on tertiles of the number of dasotraline treated subjects. Each group will contain a third of the population of dasotraline treated subjects.
- 4 equal-sized groups: 4 groups will be formed based on quartiles of the number of dasotraline treated subjects. Each group will contain a fourth of the population of dasotraline treated subjects.
- 2 equal-ranged groups: 2 groups will be formed based on the ranges of dose per weight (mg/kg) with cutoff points obtained at 2 equally spaced intervals over the range of mg/kg.
- 3 equal-ranged groups: 3 groups will be formed based on the ranges of dose per weight (mg/kg) with cutoff points obtained at 3 equally spaced intervals over the range of mg/kg.
- 4 equal-ranged groups: 4 groups will be formed based on the ranges of dose per weight (mg/kg) with cutoff points obtained at 4 equally spaced intervals over the range of mg/kg.

Each of these groupings will be analyzed using the same primary efficacy analysis method described in Section 7.5.1. In addition, each of these groupings will be analyzed for safety summarized by PT in descending order for each of the following categories: AEs, SAEs, AEs leading to discontinuation, and AEs of special concern.

A Receiver Operating Characteristic (ROC) analysis will also be conducted based on a logistic regression with dose per weight (mg/kg) as the predictor and AE of special concern as the outcome. An ROC curve for the model will be plotted. The predicted probability of having an AE of special concern event will also be plotted as a function of dose per weight (mg/kg).

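### SAP 8.5 requires adverse events of special concern to be shown only by preferred term over an open list of 55 terms; nothing requires the number of children with any such event by arm.

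*SAP*

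**What the plan says.** - **Category and display.** SAP Section 8.5 defines the events as "neuropsychiatric and mania related AEs such as ideas of reference" and continues to a total of 55 terms. The only output it names is: "AEs of special concern will be summarized by PT and treatment group".
- **Overview table.** SAP Section 8.4 plans an overview giving "the number and percentage of subjects and events with at least one of the following AEs". Its bullets cover treatment-emergent, serious, severe, related, discontinuation and fatal events. They have no line for events of special concern.
- **Counting rule.** The same section states: "Each subject will be counted only once within each SOC and within each PT". No rule counts a child once across the whole category.
- **Dose-per-weight groups.** In SAP Section 10, "each of these groupings will be analyzed for safety summarized by PT in descending order", and events of special concern are one of the categories listed there. This is again a PT display.
- **ROC model.** Section 10 also plans a logistic regression with "dose per weight (mg/kg) as the predictor and AE of special concern as the outcome". Dose per weight is calculated only for children treated with dasotraline.
- **Protocol.** The list of adverse event summaries in Section 15.3.6.1 does not include the category.
- **Contrast.** For the C-SSRS, SAP Section 8.10 does ask for a subject-level any-occurrence count, as well as separate counts for ideation and behaviour.

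**The concern.** Forming a category suggests an interest in how many children in each arm had an event belonging to it. A PT display does not answer that. The list has 11 hallucination terms and 10 delusion terms, so similar experiences in different children can be coded to different rows. A child with several terms appears in several rows. The reader then sees scattered small counts and cannot tell one child with many terms from many affected children.

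The open list adds a second problem. With *such as*, it is not settled before unblinding which events belong, so two people counting from the listings could reach different totals. Section 10 labels analyses added after SAP finalization as exploratory, so a category count added later would carry that label.

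**Working it through.** **Inputs.** SAP Section 2.4 plans about 55 children on 4 mg/day, about 55 on placebo and about 20 on 6 mg/day. The sum is 55 + 55 + 20 = 130, which reproduces the total in Section 2.6. The plan states no figure for events of special concern, so the case counts below are assumptions. All randomized children are taken as dosed, so that these are also the safety denominators.

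**1. Size of the list.** Counting the entries in Section 8.5 gives 55 distinct terms, with no duplicates. Eleven contain the word hallucination(s) and ten contain delusion or delusional.

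**2. Can PT rows be added?** Suppose six PT rows each show one child on 4 mg/day.
- Fewest children: one child with all six terms, 1/55 = 1.8%.
- Most children: six children with one term each, 6/55 = 10.9%.

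The table looks the same in both cases, so the sum of its rows does not identify the number of children.

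**3. How much a split can dilute a difference.** With *a* cases on 4 mg/day and none on placebo, 55 per arm, the two-sided Fisher p-value is 2 × C(55, a) / C(110, a).

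| Children with any event, 4 mg/day v placebo | Fisher p, any-event row | Each PT row if all terms differ |
|---|---|---|
| 3/55 v 0/55 | 0.24 | 1/55 v 0/55, p = 1.0 |
| 5/55 v 0/55 | 0.057 | 1/55 v 0/55, p = 1.0 |
| 6/55 v 0/55 | 0.027 | 1/55 v 0/55, p = 1.0 |
| 7/55 v 0/55 | 0.013 | 1/55 v 0/55, p = 1.0 |

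For *a* = 6: 2 × (55·54·53·52·51·50) / (110·109·108·107·106·105) = 2 × 0.01354 = 0.027. For a single-case row: 2 × 55/110 = 1.0.

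The Clopper-Pearson 95% interval is 4.1% to 22.2% for 6/55, and 0 to 6.5% for 0/55.

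**4. How special is the all-different assumption?** If six children each report one term, drawn with equal chance from *k* terms, the chance that all six differ is the product of (k − i)/k for i = 0 to 5. It is 0.75 for k = 55 and 0.15 for k = 10. If reports concentrate on a few common terms, some rows would hold two or more children and the dilution would be smaller.

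**5. Does another output supply the count?**
- The overview table has no line for the category.
- System organ class (SOC) totals count each child once, but are not restricted to the listed terms.
- The dose-per-weight tables are by PT.
- The ROC model needs a yes/no flag per child, but covers dasotraline-treated children only and gives no count by arm.

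**The case against.** Several points on the other side are sound.

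- **Table shells.** SAP Section 1 places table specifications in separate documents, which were not available. A by-PT table with an any-event row at the top would satisfy Section 8.5. What can be shown is that the text does not require the row, not that the final tables will lack it.
- **Recoverability.** By-subject listings of all adverse events include treatment, so the number can be counted by hand. This stands, although with an open list the hand count depends on who decides membership.
- **No comparison between arms.** A reader might infer that the plan has no randomized comparison of these events. The documents do not support that: PT rows are shown by treatment group. What is not required is a comparison of the category as a whole.
- **Only single-case rows.** A reader might infer that the table can contain nothing but zeros and ones. No event rates are given, and several children may share a term.
- **Conflicting conclusions.** A reader might infer from p = 1.0 against p = 0.027 that the two displays would lead to opposite findings. SAP Section 8.2 makes safety descriptive, so no such test is planned. Six children is also the smallest count against 0/55 that falls below 0.05. Several active-only rows beside an empty placebo column would probably be noticed.
- **Purpose.** A reader might infer that the category was set up to detect a rare class effect. Section 8.5 gives no purpose and no expected frequency.

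None of this supplies the missing requirement or closes the list.

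**Conclusion.** The point holds as a gap in specification. SAP Section 8.5 forms a category of 55 terms, leaves it open, and requires only a PT display; no SAP or protocol text requires the number of children with at least one such event by arm. That number cannot be derived from the PT rows: six single-case rows in an arm of 55 fit 1.8% to 10.9% of children. This step needs no assumption about event rates.

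The Fisher values, from 0.24 for 3 cases to 0.013 for 7, rest on assumed counts, a different term for each child, no placebo cases and full dosing of 55 per arm. They show how a split can hide a difference; they are not a forecast and not a planned test. The documents do not support saying that a signal would be missed or that the data would be lost. This is a cheap improvement to the SAP.

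**What to change.** Add to SAP Section 8.5:

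*The number and percentage of subjects with at least one treatment-emergent AE of special concern, each subject counted once, will be presented for placebo, 4 mg/day, 6 mg/day and combined dasotraline, above the PT rows.*

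Treatment-emergent should be stated because the opening definition of an adverse event in Section 8.4 also takes in events before the first dose. Exact 95% confidence intervals for each percentage are optional.

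Replace *such as* with *the following*, and allow additions only by blinded review before database lock. The same closed list should define the outcome of the ROC model in Section 10.

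Do not add separate psychosis and mania rows unless every term is assigned to one group in advance. The SAP has no such mapping, and terms such as abnormal behaviour or intrusive thoughts have no obvious place.

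**Cost.** One SAP sentence, one table row across four columns, and a short blinded review of the list. The ROC model already needs the yes/no flag for dasotraline children, so it only has to be extended to placebo. The downside is one more unadjusted descriptive safety comparison.
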